 5. Delirium
 6. Septic Shock
2. Postoperative ICU admission (yes/no)
3. Prolonged Postoperative Length of Stay (LOS) (greater than vs. less than or equal to CIHI Expected Length of Stay (ELOS) as assigned by the Case Mix Grouping) [note that the LOS includes the day of surgery]
4. Hospital readmission within 30 days (yes/no)
5. Intraoperative mortality (yes/no)
6. Days alive and out of hospital at 30 days postoperatively (28)

III. Other predictors included into model

The following potential perioperative predictors will be evaluated as covariates during model building. Statistically significant predictors will be retained in the model.

Table 2. Other predictors

Preoperative	
 1. Demographics: age on date of surgery, sex, obesity (body mass index>30) 2. Indicators of preoperative comorbidities: since no comorbidity score has perfect performance, a variety of models will be evaluated and the most significant predictive score will be retained in the model. 
 • American Society of Anesthesiologist class • RCRI score(29), and specific components via ICD codes (history of ischemic heart disease, congestive heart failure, cerebrovascular disease, diabetes, chronic kidney disease, and CCI and Case Mix Group codes of suprainguinal vascular, intraperitoneal, or intrathoracic surgery) using previously published methods (30)(31) • Elixhauser comorbidity index (32) and Charlson Comorbidity Index (33): calculated using diagnoses from the previous three years according to standard algorithm by HDNS. Reported as both total score and individual categories • Hospital Frailty Risk Score (34): based on ICD codes • Preoperative blood pressure: ICD diagnosis of hypertension and by measured blood pressure • Preoperative heart rate: Innovian and HSM • Chronic Obstructive Lung Disease (ICD code): since it may affect the interpretation of results of SpO₂ and EtCO₂ 3. Indicators of surgical complexity 
 • CIHI DAD Case Mix Group (CMG) class (also contains categories that include medical complexity) • Main Surgical Service • Procedural Index for Mortality Risk (PIMR) (35): according to CCI • Procedure: CCI codes • Preoperative ICU admission • Emergency surgery: as determined by DAD Method of Entry = emergency department or transferred from another institution)

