CIHI DAD	PATIENT_ID: encrypted health card number For HDNS internal use	Patient	Jan 1, 2013 to Dec 1, 2017	HDNS data linkage with Innovian-HSM. The dataset given to us will not contain Patient_ID, but rather a Study ID.
Vital Statistics	PATIENT_ID: encrypted health card number For HDNS internal use	Patient	Jan 1, 2013 to Dec 1, 2017	HDNS data linkage with Vital Statistics. The dataset given to us will not contain Patient_ID, but rather a Study ID.
CIHI DAD	PDATE[1-n]: procedure date	Patient	Jan 1, 2013 to Dec 1, 2017	HDNS data linkage with Innovian surgery date, to ensure that only the admission corresponding to the surgery admission of interest (first surgery admission with LOS>1) is included.

				
The PDATE matching the date of procedure (+/- 1 day) from Innovian will be used. The corresponding number (e.g. PDATE1) will be used for all procedure-related codes (e.g. PCODE1, PDSERV1).
 
Note that except for preoperative comorbidity data, where we would need data for 3 years prior to PDATE, for all other variables we only need data within 30 days after PDATE.

CIHI DAD	
LOS: Length of Stay (after surgery)
 
Derived by HDNS: discharge date minus PDATE + 1 (includes day of surgery)
	Patient	
Jan 1, 2013 to Dec 1, 2018 (to account for prolonged LOS postop from the end of inclusion date)
	
Part of inclusion criteria: if a patient had multiple surgeries, the first surgery with a LOS >1 (i.e. at least overnight stay). To calculate ratio of LOS to Expected Length of Stay (ELOS) as secondary outcome. We have chosen to standardize LOS to only include duration of stay after surgery, since there are many factors that may prolong a patient's stay prior to surgery.

Additional Demographic Information				
CIHI DAD	SEX: Patient sex	Patient	
Jan 1, 2013 to Dec 1, 2017
	
As sex may affect outcomes, this will be included as a covariate in our models
 
M = Male
 
F = Female

HSM	BMI: Body Mass Index [Derived by Innovian]	Patient	
Jan 1, 2010 to Dec 1, 2017
	
Dichotomized according to WHO definition for obesity: BMI>30. This will be combined with ICD code to create a binary Obesity variable (please see below).

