CIHI-DAD	Admit-date	Patient	1Jan2010 to 31Dec2017	
For 3-year look-back window with: either admission date or discharge date is between surgery date (B) and 3 years before B (A), assuming that A<B.
 
For 30-day follow-up window with: Either admission date or discharge date is between surgery date (B) and 30 days after B (C), assuming that B<C.

CIHI-DAD	Discharge_date	Patient	1Jan2010 to 31Dec2017	For 3-year look-back window with: either admission date or discharge date is between surgery date (B) and 3 years before B (A), assuming that A<B.

				For 30-day follow-up window with: Either admission date or discharge date is between surgery date (B) and 30 days after B (C), assuming that B<C.
CIHI DAD	ECI: Elixhauser comorbidity index [Derived by HDNS]	Patient	Jan 1, 2010 to Dec 1, 2017 (3 years before and including date of surgery)	
To be computed by the HDNS according to protocol (32) using DXCODES (please see above), to be included into model as covariate. Please report both total score, and any of the following individual categories:
 
Congestive heart failure Cardiac arrhythmias Valvular disease Pulmonary circulation disorders Peripheral vascular disorders Hypertension, uncomplicated Hypertension, complicated Paralysis Other neurological disorders Chronic pulmonary disease Diabetes, uncomplicated Diabetes, complicated Hypothyroidism Renal failure Liver disease Peptic Ulcer Disease Excluding Bleeding AIDS/HIV Lymphoma Metastatic cancer Solid tumor without metastasis Rheumatoid arthritis/ collagen vascular diseases Coagulopathy Obesity Weight loss Fluid and electrolyte disorders Blood loss anemia Deficiency anemia Alcohol abuse Drug abuse Psychoses

				Depression

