Innovian	Preoperative heart rate	Patient	Jan 1, 2013 to Dec 1, 2017	
As this may affect the level of harm from the intraoperative heart rate, it will be used in the calculation of change in heart rate (absolute and %)
 
HSM contains heart rate of elective surgery patients at the anesthetic clinic and prior to entering the operating room, while Innovian contains the initial heart rate of all patients in the operative room. The lowest heart rate from either Innovian or HSM will be used.

CIHI DAD	
Emergency surgery
 
[Derived by HDNS]
 
ENTRYCO D: method of entry
	Patient	Jan 1, 2013 to Dec 1, 2017	ENTRYCOD = E (i.e. emergency department) and/or ADFROM = [any except 085 (QEII) – i.e. transferred from another institution] excluding elective admission (flag) will be used to identify surgeries as emergency surgery. As the emergency nature of surgery has been shown to affect outcomes, it will be included as a covariate.

	ADFROM: Institution from Number			
CIHI DAD	ADTYPE: Admission Type	Patient	Jan 1, 2013 to Dec 1, 2017	This variable will be used internally by HDNS to create a flag for elective admission. This will not be included in the dataset. This will help identify patients who did not have emergency surgery.
Indicator of surgical complexity				
CIHI DAD	CMG: Case Mix Group (“a grouping methodology developed by CIHI that categorizes acute care patients into groups based on similarities of diagnosis, intervention, LOS, and resource requirements.”)	Patient	Jan 1, 2013 to Dec 1, 2017	All CMG will be included into modeling to determine the CMG with the highest postoperative risk.
CIHI DAD	PIMR: Procedural Index for Mortality Risk [Derived by HDNS]	Patient	Jan 1, 2013 to Dec 1, 2017	As the PIMR has been shown to affect outcomes, it will be included as a covariate. HDNS will calculate using DXCODE according to a published protocol (35). Detailed protocol will be sent to the HDNS.
CIHI DAD	Subgroup analysis flag: intermediate to high risk, gender neutral elective surgeries	Patient	Jan 1, 2013 to Dec 1, 2017	To create a list of intermediate to high risk, gender neutral elective surgeries for subgroup analysis. Detailed list of CCI codes will be sent to the HDNS.

	[Derived by HDNS based on PCODE]			

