CIHI DAD	
ICU admission [Derived by HDNS]
 
SCUNUM[1-n]: Special Care Unit Num “The SCU Unit Number is a code identifying the type of special care unit where the patient receives critical care.”
 
[Derived by HDNS]
	Patient	
Jan 1, 2013 to Dec 31, 2017
	
Two variables to be derived:
 
 1. Preoperative ICU (yes/no) 2. Postoperative ICU (yes/no) 
Preoperative ICU admission (yes/no) is a covariate to be included into the model. Postoperative ICU admission (yes/no) is a secondary outcome to be included into model. Descriptive statistics will be performed.
 
Derivation process: ICU = yes include the following SCUNUM: 10 = Medical Intensive Care Nursing Unit 20 = Surgical Intensive Care Nursing Unit 25 = Trauma Intensive Care Nursing Unit 30 = Combined Medical/Surgical Intensive Care Nursing Unit 35 = Burn Intensive Care Nursing Unit 40 = Cardiac Intensive Care Nursing Unit Surgery 45 = Coronary Intensive Care Nursing Unit 80 = Respirology Intensive Care Nursing Unit Else ICU = no
 
If the SCU Admit Date is on or before PDATE, then it would be defined as Preoperative AND postoperative ICU admission. Else, postoperative ICU admission only.

CIHI DAD	READMIT: Readmission Code (within 30 days after PDATE) [Derived by HDNS]	Patient	Jan 1, 2013 to Dec 31, 2017	
Readmission within 30 days of PDATE (yes/no) is a secondary outcome to be included into model. Descriptive statistics will be performed.
 
Derived: Postoperative readmission = yes include the following:
 
 1 = Planned readmission from previous acute care 2 = Unplanned readmission within 7 days following discharge from acute care 3 = Unplanned readmission 8 – 28 days following discharge from acute care 4 = ≤ 7 days, unplanned 5 = New patient 9 = None of the above. 
Else Postoperative readmission = no

CIHI DAD	LOS:EOS Ratio of Length of Stay (LOS) to Expected Length of Stay (EOS) as assigned by the Case Mix Grouping [Derived by HDNS]	Patient	Jan 1, 2013 to Dec 31, 2017	
This will be dichotomized by HDNS: LOS:EOS > 1 (yes/no). This is a secondary outcome to be included into model. Descriptive statistics will be performed.

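### The prolonged-stay outcome has no rule for death, so patients who die in hospital before their expected length of stay take its favourable value

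*Combined protocol and SAP*

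**What the plan says.** Methodology, Variables, II. Outcomes, secondary outcome 3 is "Prolonged Postoperative Length of Stay (LOS) (greater than vs. less than or equal to CIHI Expected Length of Stay (ELOS", with ELOS taken from the Case Mix Grouping.

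Appendix 1 supplies the derivation:

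- The LOS row defines LOS as "discharge date minus PDATE + 1 (includes day of surgery". It gives the reason for the clock: "We have chosen to standardize LOS to only include duration of stay after surgery", because many things can lengthen a stay before the operation. Its data span runs to Dec 1, 2018, "to account for prolonged LOS postop from the end of inclusion date".
- The LOS-to-ELOS ratio row says "This will be dichotomized by HDNS: LOS:EOS > 1 (yes/no". Its data span ends on Dec 31, 2017.
- The Discharge_date row, whose stated purpose is the three-year look-back and the 30-day follow-up windows, has the span "1Jan2010 to 31Dec2017".
- The CMG row says that the grouping "categorizes acute care patients into groups based on similarities of diagnosis, intervention, LOS, and resource requirements". It does not say which days ELOS counts.

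Data linkage, Step 2 excludes LOS of 1 or less, so a death on the day of surgery is not in the cohort. No section excludes later in-hospital deaths from the prolonged-stay outcome, recodes them, or treats them as a competing event.

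**The concern.** A short stay is a good result only if the patient leaves alive. A discharge date set by death ends the stay in the same way as a discharge home, so the rule puts early deaths in the same class as quick recoveries.

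The objective in the lay summary lists length of stay among the outcomes to be linked to vital signs. Evaluating model performance plans measures of association between hemodynamic thresholds and the secondary outcomes. The misplaced patients are the ones the study most wants to identify. If a derangement raises early mortality, part of its harm is entered on the favourable side of this outcome, and the reported association with prolonged stay no longer has a clear meaning.

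**Working it through.** **The plan's own figure.** Power calculation gives 1.7% mortality in a derivation set of 24,000: 0.017 × 24,000 = 408 deaths, and 408 / 10 = 40.8, stated as 41 predictors. This reproduces. No sizing is given for the stay outcome.

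**How a death is scored.** A death on postoperative day d has LOS = d + 1. It is not prolonged whenever d + 1 ≤ ELOS. With ELOS of 7 (assumed for illustration), in-hospital deaths on days 1 to 6 have LOS 2 to 7 and are coded not prolonged; a death on day 7 has LOS 8 and is coded prolonged. Day 0 gives LOS 1 and is excluded. A death after day 30 has LOS of at least 32, so it could be coded not prolonged only if ELOS were 32 or more. Almost all the patients concerned are therefore also 30-day deaths.

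**How many.** With 35,000 patients (Study Population) and 1.7% mortality: 0.017 × 35,000 = 595. The share dying at or before ELOS is not in the documents, so a range is assumed.

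| Share of deaths with LOS ≤ ELOS (assumed) | Patients coded not prolonged | Share of cohort |
|---|---|---|
| 25% | 149 | 0.4% |
| 50% | 298 | 0.85% |
| 75% | 446 | 1.3% |
| 100% | 595 | 1.7% |

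**Effect on an association.** Illustration with assumed inputs: in-hospital death 5% in exposed and 1.3% in unexposed patients; prolonged stay in survivors 30% and 25%. Deaths after ELOS count as prolonged, as the rule implies.

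- Survivors only: (0.30/0.70) / (0.25/0.75) = 1.29.
- As scored, all deaths early: exposed 0.95 × 0.30 = 0.285; unexposed 0.987 × 0.25 = 0.24675; odds ratio (0.285/0.715) / (0.24675/0.75325) = 1.22.
- As scored, half of deaths early: exposed 0.285 + 0.025 = 0.310; unexposed 0.24675 + 0.0065 = 0.25325; odds ratio (0.310/0.690) / (0.25325/0.74675) = 1.32.
- Every death counted as a bad outcome: exposed 0.285 + 0.05 = 0.335; unexposed 0.24675 + 0.013 = 0.25975; odds ratio (0.335/0.665) / (0.25975/0.74025) = 1.44.

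The scored result depends on when deaths happen. It lies below the death-counted result in both scored cases, and on either side of the survivor result.

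**ELOS clock.** If ELOS covers the whole hospitalization (not stated), a patient with p preoperative days is scored not prolonged although the total stay exceeds ELOS when LOS ≤ ELOS < p + LOS. With ELOS 7 and p = 5, that is LOS 3 to 7 (5 + 3 = 8 > 7). With p = 0 there is no shift.

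**Data spans.** For surgery on the last eligible date, Dec 1, 2017, the longest observable LOS is 31 days with data to Dec 31, 2017 and 366 days with data to Dec 1, 2018. Under the shorter span, anyone still in hospital on Dec 31, 2017 already has LOS of at least 31. The class is then unknown only if ELOS is 31 or more, provided the record is retrieved at all.

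**The case against.** The strongest reply is that the matter is small and largely covered. At most 1.7% of patients are affected. Death is the primary outcome, days alive and out of hospital at 30 days is already a secondary outcome that joins death to hospital days, and deaths are to be described by location and day. The Hypothesis section names mortality and morbidity, not length of stay. A composite of stay and death is one option among several. All of this stands as mitigation, and it is why no single replacement endpoint is insisted on. It does not repair the stay variable, which will be modelled and reported in its own right.

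A reader might also infer four stronger things that the documents do not support:

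- *That lethal derangements will look protective.* The illustration shows distortion, not reversal. Even with no effect in survivors (25% prolonged in both groups), the scored odds ratio is (0.2625/0.7375) / (0.25325/0.74675) = 1.05 if half of deaths are early. It falls below 1, to (0.2375/0.7625) / (0.24675/0.75325) = 0.95, only in the case where all are.
- *That readmission has the same fault.* The READMIT row says "Readmission within 30 days of PDATE (yes/no) is a secondary outcome to be included into model", but the codes printed under yes include new patients and none of the above. The text does not settle how a death would be scored.
- *That LOS and ELOS certainly count different days.* The postoperative count is explicit and reasoned. The ELOS clock is never stated. A whole-stay ELOS is a fair inference from a hospitalization-level database, but only an inference.
- *That discharge data stop too early.* The LOS row already runs to Dec 1, 2018 for this purpose, and the Discharge_date row serves other windows. What remains is a conflict between rows.

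**Conclusion.** The point holds for the missing death rule. In-hospital deaths after the day of surgery with LOS at or below ELOS are coded not prolonged. The ceiling is 595 patients, with about 149 to 446 under the assumed 25% to 75% share. These counts take the plan's provincial 1.7% in-hospital rate as the cohort rate and ignore the removal of day-of-surgery deaths, so 595 is an upper figure at that rate. Associations with prolonged stay are distorted relative to counting death as a bad outcome; the direction relative to survivors depends on the timing of deaths, which the documents do not give.

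The ELOS clock and the data spans are secondary points for clarification. The first matters only if ELOS includes preoperative days. The second could leave a class undetermined only for long-stay patients from late 2017 whose ELOS is itself 31 days or more, or whose record is not retrieved.

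**What to change.** Add a death rule to secondary outcome 3 and to the ratio row of Appendix 1, before data extraction. Either of these would do:

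1. Analyse prolonged stay in patients discharged alive, and show in-hospital death by exposure beside it.
2. Score prolonged stay or in-hospital death as the event, and report the two parts separately.

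Appendix 1 already requests in-hospital death and postoperative day of death. The in-hospital death flag is described for deaths within 30 days, so its wording should be widened to the whole index stay. The cost is a few lines of derivation wording. The downside is a restricted population under option 1, since survival is itself affected by exposure, or a mixed endpoint under option 2, which reporting both parts addresses.

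Also:

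- Confirm with the data custodian which days ELOS counts, and state it. If it covers the whole hospitalization, compare like with like, for example postoperative LOS against a CMG-specific postoperative reference estimated in the derivation set. This keeps the deliberate choice to ignore preoperative days.
- Reconcile the LOS span (to Dec 1, 2018) with the Discharge_date and ratio spans (to Dec 31, 2017), so that the extraction follows one date.

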The results of this study may help synthesize complex intraoperative clinical information and unveil novel therapeutic strategies. Derived from data from the QEII Hospitals, the results would be directly applicable to the care of Nova Scotians. The models may lead to the creation of objective risk stratification scores calculated at the end of surgery, to identify high risk patients for increased postoperative follow-up and monitoring. Moreover, if models created using machine learning perform well, machine learning may be used more frequently to reveal the patterns within complex, large perioperative datasets. Hemodynamics are potentially modifiable risk factors. Future research includes prospective studies on whether targeted hemodynamic goals, increased postoperative follow-up of high-risk patients, and real-time machine learning precision medicine could improve outcomes after surgeries.

Specific aims

1. To use machine learning techniques to investigate systematically intraoperative hemodynamic predictors of postoperative 30-day all-cause mortality (primary outcome) and major in-hospital morbidity. Hemodynamic predictors to be studied are blood pressure, heart rate, oxygen saturation, end-tidal carbon dioxide, and medications to adjust blood pressure. Please see “Outcomes” section below for full list of secondary outcomes.
2. To evaluate performance of machine learning models created and compare the performance of the best model to the Surgical Apgar Score.

Hypothesis

Controlling for other predictors, the durations of mean arterial pressure (MAP) <65mmHg, heart rate <60 or >100 beats per minute (BPM), hemodynamic medications use, oxygen saturation (SpO₂) <88%, and end-tidal carbon dioxide (EtCO₂) <30 or >45 will be associated with postoperative 30-day all-cause mortality (primary hypothesis) and 30-day major in-hospital morbidity (secondary hypothesis). Note that blood pressure, heart rate, vasopressors and

inotropic medications, oxygen saturation, and end-tidal are considered key indicators of hemodynamics. We have chosen conventional ranges commonly used in practice, and will perform sensitivity analysis of different definitions of each hemodynamic variable.

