At the time of surgery, anesthesiologists document the timing of key clinic information (induction, intubation, start and end of surgery, emergence, extubation, and exit of the operating room), medications and fluids administered, estimated blood loss, and type of anesthesia into the intraoperative record. Hemodynamic factors are automatically recorded into the database every minute. The following intraoperative hemodynamic factors will be included in model building:

Table 1. Exposures

Blood pressure	
Since there is no universal definition of low blood pressure under anesthesia, we will use several different variables to determine the most significant exposure by threshold and duration. Both Systolic Blood Pressure (SBP) and Mean arterial pressure (MAP) have been used in blood pressure research (12). In a recent study (26), different blood pressure modeling techniques on the same dataset led to different conclusions on the impact of hypotension on postoperative myocardial infarction and kidney injury. Methods with the largest odds ratios were absolute maximum decrease in MAP and mean episode area under threshold. However, since the area under threshold is less interpretable and difficult to calculate in everyday clinical practice, the duration under threshold will be used.
 
SBP
 
1. Maximum change from preoperative SBP, in a) absolute change (mmHg), and b) relative change (%) (emergency and elective cases analyzed separately due to the lack of preoperative blood pressure in the emergency group)2. Cumulative duration (minutes) $\geq 20\%$ below preoperative SBP3. Longest single episode (minutes) below a) 80, b) 90, and c) 100 mmHg4. Cumulative duration (minutes) below a) 80, b) 90, and c) 100 mmHg 
MAP
 
1. Maximum change from preoperative MAP, in a) absolute change (mmHg), and b) relative change (%) (emergency and elective cases analyzed separately due to the lack of preoperative blood pressure in the emergency group. Note that since the HSM database only contains SBP and DBP, not MAP, MAP will be calculated using $MAP = 1/3*SBP + 2/3*DBP$)2. Cumulative duration (minutes) $\geq 20\%$ below preoperative MAP3. Longest single episode (minutes) below a) 60, b) 65, c) 70, and d) 80mmHg4. Cumulative duration (minutes) below a) 60, b) 65, c) 70, and d) 80mmHg
-----------------------	---

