The performance of all models created will be evaluated in the validation set as part of internal validation using the same metrics of discrimination, calibration, and risk reclassification, and compared to the Surgical Apgar Score. Since there will likely be significant class imbalance and ROC curves may overestimate model performance, for each model, precision and recall curves (PRC), F score, average precision, and AUC will also be reported and compared. The best performing model will also be used to analyze for predictors for secondary outcomes. Sensitivity (recall, true positive rate), specificity, positive predictive value (precision), G-mean, negative predictive values, False Discovery Rates (FDR), optimism, and measures of association of hemodynamic thresholds for primary and secondary outcomes will be computed. Bayesian network causal inference analysis may be performed, to help increase interpretability.

Sensitivity and subgroup analysis

Sensitivity analysis will be performed for different definitions of hemodynamic derangements. Subgroup analysis will be performed based on age, sex, high preoperative risk (most significant indicator of preoperative comorbidity in Table 2, based on final model), RCRI, frailty (HFRS), preoperative hypertension, a select list of intermediate-high risk, gender-neutral elective surgery (please see Appendix – RCRI Protocol Table 1), emergency surgery, and type of anesthesia.

Power calculation

The 2016-2017 in-hospital mortality after major surgery in Nova Scotia is 1.7% (47). Using the Events Per Variable criterion (EPV) of at least 10 outcomes per predictor in the sample, the 1.7% mortality (408) out of an estimated sample size of 24,000 for the derivation/training group means that our model would be valid for up to 41 predictors for the primary outcome. However, the EPV may over or underestimate the limitations of the EPV criterion (48), square root of the mean squared prediction error (rMPSE) and mean absolute prediction error (MAPE) will be calculated based on the number of predictors, sample size and events fraction (49) with the caveat that this model has not been externally validated. Full power calculation will be performed once we receive the final sample size.

Strengths

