Innovian	SpO₂: Oxygen saturation by pulse oximetry [Derived by Innovian as multiple variables – see right]	Patient	Jan 1, 2013 to Dec 1, 2017	
Exposure variable to be included into modeling. The following variables will be derived by Innovian:
 
3. Longest single episode (minutes) below a) 88, and b) 90%
 
4. Cumulative duration (minutes) below a) 88, and b) 90%

Innovian	EtCO₂: End-tidal (i.e. exhaled) [Derived by Innovian as multiple variables – see right]	Patient	Jan 1, 2013 to Dec 1, 2017	
Exposure variable to be included into modeling. The following variables will be derived by Innovian:
 
1. Longest single episode (minutes) a) <35, and b) >45
 
2. Cumulative duration (minutes) below a) <35, and b) >45

HSM	Duration of surgery	Patient	Jan 1, 2013 to Dec 1, 2017	As this may affect outcomes, it will be included as a covariate
Innovian	Type of anesthesia	Patient	Jan 1, 2013 to Dec 1, 2017	Categorical variable: general, neuraxial, peripheral nerve block, and/or managed anesthesia care [i.e.

				
sedation] – multiple concurrent possible). As this may affect outcomes, it will be included as a covariate.
 
Innovian will be used instead of the CIHI ANATYP (Anaesthetic Type), since anesthetic type is a mandatory field in Innovian and will allow for multiple concurrent anesthetic types.

Innovian	Average MAC-adjusted: Minimal Alveolar Concentration adjusted by age [Derived by Innovian]	Patient	Jan 1, 2013 to Dec 1, 2017	Age-adjusted MAC will be calculated by Innovian from the end-tidal % of all inspired volatiles according to published protocol (36). The MAC, available every 15 seconds will be averaged (i.e. time-averaged MAC). The averaged MAC will be included as a covariate.
Innovian	BIS : Bi-spectral Index [Derived by Innovian]	Patient	Jan 1, 2013 to Dec 1, 2017	Duration in minutes for BIS <46. As deep anesthesia (low BIS) may affect outcomes (50), it will be included as a covariate.
Innovian	Laparoscopy-booked [Derived by Innovian]	Patient	Jan 1, 2013 to Dec 1, 2017	Binary variable (yes/no), as defined by “laparoscope” or “laparoscopic” in procedure name.
DAD	Laparoscopy converted to open flag STATUS[1-n] [Flag by HDNS]	Patient	Jan 1, 2013 to Dec 1, 2017	
Flag: STATUS[1-n] = C “Converted from endoscopic to open”
 
Since Innovian procedure names are usually from OR booking, procedures where laparoscopy was converted to open would be included in the laparoscopy (booked) variable.

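### Covariates are kept by statistical significance, and the plan does not say which blood pressure definition or which data set the primary association estimate rests on

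*Combined protocol and SAP*

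**What the plan says.** All references are to the combined protocol and SAP.

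- **Adjustment.** The Hypothesis section poses an association adjusted for other predictors. Under Variables, III (Table 2), the rule for those predictors is "Statistically significant predictors will be retained in the model". For the comorbidity measure, "a variety of models will be evaluated and the most significant predictive score will be retained in the model". No significance level is given for either step.
- **Exposure definitions.** The Hypothesis section names "the durations of mean arterial pressure (MAP) <65mmHg, heart rate <60 or >100 beats per minute (BPM), hemodynamic medications use, oxygen saturation" and EtCO₂ limits, and adds: "We have chosen conventional ranges commonly used in practice, and will perform sensitivity analysis of different definitions of each hemodynamic variable". The Sensitivity and subgroup analysis section repeats that role for alternative definitions. The blood pressure row of Table 1 says something else: "we will use several different variables to determine the most significant exposure by threshold and duration".
- **Selection method.** Creating the models gives LASSO and Elastic Net as examples of variable selection in the logistic model.
- **Estimation.** Evaluating model performance says that "measures of association of hemodynamic thresholds for primary and secondary outcomes will be computed", without naming the data set, alpha, or any allowance for selection. The later-period validation set is described for model performance.
- **Low EtCO₂.** The limit is <30 in the Hypothesis section and Table 1. The EtCO₂ row of Appendix 1 has "Longest single episode (minutes) a) <35, and b) >45".

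**The concern.** The study has a prediction aim and an association aim. Selecting predictors by their data fit can be defended for prediction, where the held-out period checks performance. It is a poor basis for an adjusted association. A confounder that misses significance is dropped although it still biases the exposure estimate, and the remaining p-values and intervals take no account of the selection. Choosing the most significant of several overlapping exposure definitions has a similar effect: the winner's estimate is inflated and its p-value understated.

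The lay summary aims to say which vital signs, at what levels, may be harmful, and Future directions proposes randomized studies of hemodynamic targets. Those uses depend on the association estimates. The Limitations section relies on multivariable adjustment to deal with confounding, which is the step that the retention rule weakens.

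**Working it through.** **The plan's own figure.** Power calculation: 24,000 × 0.017 = 408 deaths in the derivation set, and 408 / 10 = 40.8, given as 41 predictors. Both reproduce.

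**Number of definitions in Table 1.**
- MAP: 2 maximum changes + 1 relative duration + 4 longest episodes + 4 cumulative durations = 11.
- SBP: 2 + 1 + 3 + 3 = 9.
- Heart rate 7, medications 5, SpO₂ 4, EtCO₂ 4.
- Total: 11 + 9 + 7 + 5 + 4 + 4 = 40, so the exposures alone almost fill the limit of 41 before any covariate enters.

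**Effect of picking the best definition.** Assumptions, none of them in the plan: two-sided alpha 0.05, no true effect, selection and testing on the same data. For k independent definitions, P(smallest p < 0.05) = 1 − 0.95^k; for k = 11 this is 43.1%. The definitions overlap, so the relevant figure is lower. With jointly normal test statistics of equal pairwise correlation, simulation for k = 11 gives:

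| Correlation | P(best p < 0.05) |
|---|---|
| 0.5 | about 30% |
| 0.7 | about 22% |
| 0.9 | about 13% |

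A second check simulated autoregressive pressure series for 24,000 patients with 408 random deaths:

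| What is tested | P(p < 0.05) |
|---|---|
| Cumulative minutes with MAP <65, fixed in advance | 5.2% |
| Best of the 8 MAP threshold durations | 13.8% |
| Best of all 11 MAP definitions | 20.7% |
| Best of all 20 MAP and SBP definitions | 30.0% |

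For the effect estimate, take 8 definitions, correlation 0.8 and a true z of 2. The winning z averages 2.62, and 2.62 / 2 = 1.31, so it is 31% too large. The nominal 95% interval covers 90.6% of the time.

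**Effect of dropping confounders.** This is a separate calculation; the figures above say nothing about it. Information per standardized covariate = 24,000 × 0.017 × 0.983 = 401, so SE = 1/√401 = 0.050. For a confounder with odds ratio 1.10 per SD, ln(1.10) / 0.050 = 1.91, and the chance of p<0.05 is about 48%. A confounder of that strength is dropped about half the time. Under a null exposure, suppose all confounders push the same way, with odds ratio 1.05 to 1.15 per SD, correlation 0.1 to 0.3 with the exposure, and 0 to 0.2 among themselves:

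| Confounders at risk of being dropped | Type I error after selection | Mean exposure odds ratio (truth 1.00) |
|---|---|---|
| 1 | 4.8–7.0% | 1.00–1.01 |
| 5 | 6.2–17.6% | 1.01–1.04 |
| 10 | 7.8–36.1% | 1.02–1.08 |

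With the full set kept regardless of p-value, type I error was 4.7–5.3% throughout.

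**Estimating in the validation set only.** If 24,000 is 80% of the cohort, the total is 30,000, and 20% × 30,000 × 0.017 = 102 deaths. With the stated cohort of about 35,000, 20% × 35,000 × 0.017 = 119. Against 408 deaths, the SE ratio is √(408/102) = 2.0 or √(408/119) = 1.85.

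**The case against.** A reader might infer that the plan abandons its hypothesis thresholds and reports odds ratios from the same fit that selected them. The documents do not support that.

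- The thresholds are fixed in the Hypothesis section, and two places call other definitions sensitivity analyses. A test confined to the fixed thresholds carries no threshold-search bias. The pick-the-most-significant wording is in the blood pressure row only; Table 1 gives no such rule for heart rate, SpO₂ or EtCO₂. What stands is a conflict between two sections.
- No sentence says that associations come from the selection data. The sentence promising them is in a paragraph that opens with the validation set and also lists optimism. Estimation in the derivation set, where the models are built, is a natural reading but an inference. What stands is that the data set is unstated.
- LASSO and Elastic Net do not select by p-value. They are named only as examples, however, and do not fit the Table 2 retention rule. Ordinary p-values computed after penalized selection also ignore the selection.
- The 13–30% concerns the MAP definition search, not covariate retention. With few weak confounders, the bias from retention is slight.

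None of this removes the covariate rule, which would affect a test of the fixed thresholds too.

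**Conclusion.** The concern holds in limited form. Retention of covariates and of the comorbidity score by significance is explicit and uncorrected, and it applies to an adjusted association hypothesis. The role of the alternative blood pressure definitions is contradictory, and the estimation data set and alpha are missing.

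The size is conditional. If the best MAP definition is selected and tested on the same data at two-sided 0.05, the false-positive rate is about 13–30% for correlations of 0.9 to 0.5. It is 5% if MAP <65 is fixed in advance in one stated form. The harm from dropped confounders ranges from negligible to substantial according to their number and strength, which the documents do not give. The prediction aim is affected much less, because the held-out period checks performance. This should be settled before analysis, but it does not invalidate the study.

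**What to change.** 1. Test the primary hypothesis in one prespecified logistic model using the Hypothesis thresholds. State cumulative duration or longest episode for each exposure, and which of the five medication variables is meant.
2. Reconcile the lower EtCO₂ limit across the Hypothesis section, Table 1 and Appendix 1. Because EtCO₂ is analyzed only under general anesthesia, say how other cases enter the model.
3. Fix the confounder set in advance from Table 2 on subject-matter grounds and keep it whatever the p-values. An example is age, sex, ASA class, one named comorbidity index, COPD, PIMR, surgical service, preoperative ICU admission, emergency status, anesthesia type and surgery duration. Give a reason for including or omitting blood loss, transfusion and postoperative hemoglobin. Count all model terms, including splines, against the 41.
4. State alpha and the data set used for the association estimates.
5. Keep LASSO or Elastic Net and the threshold search for the prediction aim, and reword the Table 2 retention rule to match. Label the search exploratory and report its estimates with a bootstrap that repeats the whole selection. Estimating in the validation set alone is the weaker choice, since about 102–119 deaths would roughly double the standard error.

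The cost is SAP wording, one extra model on data already requested, the computing time for the bootstrap, and somewhat wider intervals for the main associations.
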